CooperVision is evaluating the clinical performance of an investigational silicone-hydrogel lens referred to as the Invigor I (test) compared to the clariti lens (control) when worn on a daily wear basis over one-month for each lens type in a randomized, bilateral, cross-over, dispensing study.

[REDACTED]

2 Study Objective

This is a study to evaluate the clinical performance of the Invigor I lens when worn on a daily wear modality over one-month usage.

The primary variables of interest are:

- Lens surface wettability and surface deposits
- Lens fit performance

The secondary variable of interest is:

- Anterior ocular physiological response

[REDACTED]

[REDACTED]

[REDACTED]

3 Study Design

This will be a randomized, multicenter, bilateral, one month cross-over, double-masked, dispensing study comparing the Invigor I test lens against the clariti control lens. Each subject will be randomized to wear either the test or control as a matched pair first with a study duration of approximately two months. Both test and control lenses will be used in a daily wear modality for one month. There will be no planned lens replacement during the course of the one-month study unless due to lens damage/defects. It is anticipated that this study will involve up to 5 visits: Baseline (screening and dispense the first pair visit), 2-week follow-up visit for the first pair, one-month follow-up visit for the first pair and dispense the second pair, 2-week follow-up visit for the second pair, and one-month follow-up visit for the second pair and exit visit.

4 Ethics Review / Statement of Compliance

4.1 Relevant Standards / Guidelines

This implementation document has been developed in accordance with the following:

- ISO 14155 Clinical Investigation of Medical Devices for Human Subjects
- 21 CFR 812.2(b) Investigational Device Exemption – Abbreviated Requirements
- ISO 11980 Contact Lens and Lens Care products – Guidance for Clinical Investigations
- ICH Harmonized Tripartite Guideline for Good Clinical Practice
- Declaration of Helsinki

4.2 Institutional Review Board

This study will be conducted in accordance with Institutional Review Board regulations (U.S. 21CFR Part 56.103) or applicable IEC regulations. Copies of all IRB/IEC correspondence with the investigator/sponsor will be kept on file.

The conduct of this study will occur at two sites, CORL at Indiana University and CRC at the University of California, Berkeley. The conduct of this study will be approved for each site by an Institutional Review Board prior to commencement.

4.3 Informed Consent

Informed consent shall be obtained in writing from the subject and the process shall be documented before any procedure specific to the clinical investigation is carried out.

5 Clinical Trial Registration

This Study will be registered with ClinicalTrials.gov in accordance with Section 801 of the Food and Drug Administration Act (FDAA) which mandates the registration of certain clinical trials of drugs and medical devices.

[REDACTED]

[REDACTED]

[REDACTED]

[REDACTED]

[REDACTED]

[REDACTED]

7 Materials and Methods

7.1 Subjects

This study will recruit at two clinical sites, the Clinical Optics Research Lab (CORL) at Indiana University and UC Berkeley Clinical Research Center (CRC). Up to 80 subjects will be dispensed across both sites with the aim of completing 60 subjects across both sites. Each subject will be given a unique ID number. Subject ID numbers will be assigned to the subjects sequentially and in ascending order, and will not be reused in the event of screen failure, subject dropout or discontinuation from the study.

Potential subjects will be identified from the investigators' clinic and research database records and/or will be actively recruited by advertisements circulated at the investigational sites as approved by the appropriate IRB.

There are no provisions for replacing subjects during the study who are discontinued from the study.

Additionally, all subjects must meet the study inclusion and exclusion criteria listed below.

Inclusion Criteria

A person is eligible for inclusion in the study if he/she:

- Has had a self-reported oculo-visual examination in the last two years.
- Is at least 18 years of age and has full legal capacity to volunteer.
- Has read and understood the information consent letter.
- Is willing and able to follow instructions and maintain the appointment schedule.
- Is correctable to a visual acuity of 20/40 or better (in each eye) with their habitual vision correction or 20/20 best-corrected.
- Currently wears soft contact lenses.
- Requires spectacle lens powers between -0.75 to -6.50 diopters sphere (0.25D steps).
- Has no more than 0.75 diopters of refractive astigmatism.
- Has clear corneas and no active ocular disease.
- Has not worn lenses for at least 12 hours before the examination.
- Has a usable pair of spectacle lenses if required for transportation to the site for the initial visit

Exclusion Criteria

A person will be excluded from the study if he/she:

- Has never worn contact lenses before.
- Has any systemic disease affecting ocular health.
- Is using any systemic or topical medications that will affect ocular health.
- Has any ocular pathology or severe insufficiency of lacrimal secretion (moderate to severe dry eyes) that would affect the wearing of contact lenses.
- Has persistent, clinically significant corneal or conjunctival staining using sodium fluorescein dye.
- Has any clinically significant lid or conjunctival abnormalities, active neovascularization or any central corneal scars.
- Is aphakic.
- Has undergone corneal refractive surgery.
- Is participating in any other type of eye related clinical or research study.
- Known allergy to a product used in this study (ex. Shellfish allergy)
- Is pregnant, lactating or planning a pregnancy at the time of enrolment (by verbal confirmation at the screening visit).

7.2 Number of Sites

The study will be take place at two sites: Indiana University School of Optometry within the Clinical Optics Research Lab (CORL) and UC Berkeley School of Optometry Clinical Research Center (CRC). These sites were selected based on the experience of their site investigators and staff in conducting clinical trials, the availability of potential study subjects, and the interest of the sites in performing the trial. A site investigator agreement and financial disclosure document will be in place prior to commencement of the trial.

7.3 Study Materials

7.3.1 Contact lens

Subjects will be randomized to receive either Test and Control lens as the first pair of contact lenses as per the randomization schedule. The lenses used in this study will be provided by the sponsor.

Both the Test and Control lenses will be labelled with “Investigational” wording on the labels for study masking purpose. The Test lens is an investigational product. It will be subject to preclinical assessment before being released for the study. The clariti contact lens material (somofilcon A) is FDA-cleared and is commercially available in the USA.

Details of the contact lenses are shown in Table 1.

Table 1: Study lenses

	Invigor I (Test)	clariti (Control)
Material	██████████	somofilcon A
Base Curve (mm)	8.6	8.6
Lens Diameter (mm)	14.2	14.2
Power (D)	-1.00 to -6.00 (0.25 steps)	-1.00 to -6.00 (0.25 steps)
Wear regimen	Daily wear	Daily wear

7.3.2 Contact Lens care

Subjects will be provided with an approved marketed lens care solution. The subject will be trained on how to use the care solution. The lens care products will be provided by the site.

7.3.3 Contact Lens Dispensing

The lenses will be inserted directly from the blister pack. The use of saline for rinsing prior to insertion is permitted if necessary. Saline will not be dispensed during the study. Subjects will not be allowed to use rewetting drops during the study.

7.3.4 Storage of Lenses and Lens Care Solutions

The study materials must be stored in a secure area and administered only by an unmasked study coordinator. It is recommended that all lenses and solutions be stored at controlled room temperature (59-86°F).

7.3.5 Clinical Supply Inventory

The investigator must keep an accurate accounting of the study product during the study. A detailed inventory must be completed for study supplies. The study supplies are to be used in accordance with the implementation document by subjects who are under the direct supervision of an investigator.

The subject will be issued with a pair of spare contact lenses in a sealed envelope to protect masking, along with the study supplies.

In the event that a lens in one eye needs to be replaced due to damage/defects before the one-month visit, only the damaged/defective lens will be replaced (e.g. not the lens in the other eye). A log of lens replacement will be recorded by the site. Subjects will be asked to keep and return the 'damaged/defective' lens.

7.3.6 Disposal of Consumables

This study dispenses consumables (lenses) to subject for use during the study. Study solutions used and/or study lenses worn by subject will be collected in lens cases stored in non-preserved saline solution and returned to the sponsor at the completion of the study. Leftover solution and cases will be disposed of either by the subject or by the clinical site staff. Lenses with product observations (e.g. moderate lens deposits), product defects, or product quality complaints will be collected and returned to the sponsor at the completion of the study.

7.3.7 Masking and Control of Study Materials

The contact lenses coding will be masked to both the investigator and subject.

Under normal circumstances, the mask will not be broken until all subjects have completed the study and the database is finalized. Otherwise, the mask should be broken only if a specific emergency treatment or course of action would be dictated by knowing the treatment status of the subject. In such cases, the investigator may contact CVI in an emergency to request this information. In the event the mask is broken, the sponsor must be informed as soon as possible. The date, time, and reason for the unmasking must be documented.

7.3.8 Ordering and Accountability of Study Materials

The test and control lenses will be provided by the sponsor.

The investigator must complete an accurate accounting of the study product at the completion of the study. A detailed inventory must be completed for study supplies.

All unused and used materials will be returned to the sponsor at the end of the study unless the investigator is otherwise directed by the study sponsor.

7.4 Visit Schedule and Procedures

Prior to lens insertion biomicroscopy (including corneal and conjunctival staining) will be completed at the screening assessment. When possible, the screening will be combined with the baseline assessment. The investigator should confirm with the subject that they are able to attend the follow-up visits within the visit window before enrolling them in the study.

A scheduled follow-up visit of lens assessment/s may only take place when the subject attends wearing the study lenses. If this is not the case and the subject is not experiencing any problems with the lenses, the appointment will be rescheduled, ideally within the visit window unless they are experiencing difficulty.

Visits that fall outside of the specified visit windows will be counted as unscheduled visits for analysis purposes. In addition to the screening visit, subjects will attend four visits (not including any unscheduled visits) and will wear the test or control lenses according to the study design.

There will be a minimum of five scheduled visits as follows:

Visit 1: Baseline/Screening/Dispensing Pair 1 (Day 0)

Visit 2: Two week follow up for Pair 1 (Day 14 ± 3)

Visit 3: One month follow up for Pair 1/Dispensing Pair 2 (Day 28 ± 4)

Visit 4: Two week follow up for Pair 2 (Day 14 ± 3)

Visit 5: One month follow up for Pair 2/Exit visit (Day 28 ± 4)

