- 3. [REDACTED]
- 4. [REDACTED]

[REDACTED]

5. Monocular lens surface will then be assessed and graded according to CVI grading scales (Appendix 2).

- [REDACTED]
- [REDACTED]
- c. Lens wettability (0-4 scale)
- [REDACTED]
- [REDACTED]

- f. Lens deposition (0-4) and deposit type
- [REDACTED]

[REDACTED]

6. Monocular lens fit will then be assessed and graded according to CVI grading scales (Appendix 2).

[REDACTED]

b. Lens centration (optimal /slightly decentered, <0.5mm /extremely decentered >0.5mm, NTSI)

[REDACTED]

[REDACTED]

[REDACTED]

[REDACTED]

[REDACTED]

[REDACTED]

[REDACTED]

i. Overall lens fit acceptance (0-4 scale, and yes/no) and investigator reason, if unacceptable.

- [REDACTED]
- [REDACTED]
8. Slit lamp biomicroscopy will be assessed according to the guidelines set out in the CVI Grading scales.
9. There will be a 10-minute wash-out before insertion of pair 2.

Lens Dispensing Pair # 2

1. The second lens pair will be applied (according to the randomization table). The contact lenses will be provided by a study coordinator/technician to maintain masking of the investigator. The lenses will be inserted by the subject from the blister pack.
2. The use of saline for rinsing prior to insertion is permitted if necessary.
3. Lens powers of the second pair will be matched with the first pair if possible.

Procedures will be repeated as detailed in Visit 1 for pair 2 from section 7.4.1 (steps 1-13 in Dispensing pair#1 section).

7.4.4 Visit 4: Two-week follow up of pair #2 (Day 14 ± 3 of pair 2)

*Subjects will be asked to wear lenses for **at least 2 hours** prior to the visit appointment. Subjects who attend without lenses in situ for at least two hours will be rescheduled.*

Procedures will be repeated as detailed from section 7.4.2 for pair 2 (steps 1-9).

7.4.5 Visit 5: One Month Visit Pair 2/Study Exit (Day 28 ± 4 of pair 2)

Subjects will be asked to wear lenses for at least 2 hours prior to the visit appointment. Subjects who attend without lenses in situ for at least two hours will be rescheduled.

Procedures will be repeated as detailed from section 7.4.3 (steps 1-8).

[REDACTED]

[figure not shown]
- 1. [REDACTED]
- 2. [REDACTED]
- 3. [REDACTED]
- 4. [REDACTED]

[REDACTED]

3. Slit lamp biomicroscopy assessment will be conducted according to the guidelines set out in the CVI Grading scales
4. Exit visual acuity with habitual spectacles or spectacle refraction (using same method and refraction as entry).

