10.2 Statistical analysis

De-identified data will be provided to the sponsor by each site for the sponsor to perform the analyses. Each site will only have access to the data collected at their site.

Summary statistics will be produced (e.g. mean, standard deviation). Non-inferiority testing will be performed as appropriate. Paired t test will be used to compare slit lamp biomicroscopy, lens fit and subjective scores between study lens types. Repeated Measures Analysis of Variance (ANOVA) or paired analysis will be used to compare the variables between study visits. The critical level for statistical significance will be set at $p \leq 0.05$.

All participants who were evaluated will be used in the analysis. In the event of missing data, individual data points will be excluded in the analysis and not extrapolated from the collected data. A detailed statistical analysis plan will be outlined in the report.

11 Data Quality Assurance

[REDACTED]

[REDACTED]

[REDACTED]

[REDACTED]

- [REDACTED]
- [REDACTED]
- [REDACTED]
- [REDACTED]
- [REDACTED]
- [REDACTED]

[REDACTED]

[REDACTED]

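### Does counting out-of-window follow-ups as unscheduled take observed values out of the lens comparison?

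*Combined protocol and SAP*

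**What the plan says.** Section 7.4 lists five visits. The two-week visits have a window of ± 3 days around Day 14, and the one-month visits ± 4 days around Day 28. It then gives the rule at issue: "Visits that fall outside of the specified visit windows will be counted as unscheduled visits for analysis purposes". The next sentence uses the same term when counting attendance: after screening, "subjects will attend four visits (not including any unscheduled visits").

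For a subject who attends without the study lenses and has no problem with them, "the appointment will be rescheduled, ideally within the visit window unless they are experiencing difficulty".

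The list in 7.4 shows the double visit as "Visit 3: One month follow up for Pair 1/Dispensing Pair 2 (Day 28 ± 4"). Section 7.4.3 says of the second pair: "Procedures will be repeated as detailed in Visit 1 for pair 2 from section 7.4.1".

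Section 10.2 is the only visible text on methods of analysis. It states: "Paired t test will be used to compare slit lamp biomicroscopy, lens fit and subjective scores between study lens types", and for change over time: "Repeated Measures Analysis of Variance (ANOVA) or paired analysis will be used to compare the variables between study visits". On who is analysed it says: "All participants who were evaluated will be used in the analysis". It leaves out individual points where data are missing, does not impute, and defers a detailed analysis plan to the report. It does not mention unscheduled or out-of-window visits. Parts of section 7.4 are redacted; the text of 10.1 and 10.2 shows no redaction.

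**The concern.** The rule in 7.4 is worded as an analysis rule, yet its effect is not given. If an unscheduled visit is not a one-month visit, a value from day 33 is not a one-month value. A paired t test at one month needs a value under each lens, so that subject would drop out although both lenses had been assessed. The data affected would include the primary variables (surface wettability, deposits and fit) and the slit lamp findings.

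Visit 3 adds a second worry. It closes Pair 1 and dispenses Pair 2, so a late Visit 3 might seem to make the Pair 2 dispensing grades unscheduled too.

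At stake would be some precision, and a choice left open until the analysis is written up.

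**Working it through.** **1. Reproduce the plan's own figure.** Table 3 in section 10.1 gives a mean difference of 0.5, a standard deviation of 1.3 and alpha 0.05. Sidedness is not stated; two-sided is assumed. With a paired t test and the noncentral t distribution (noncentrality 0.5/1.3 × √n), the smallest n is 56 for 80% power (0.807) and 63 for 85% (0.852). Both match Table 3. The normal approximation, (1.3 × (z for alpha + z for power)/0.5)², gives 53.06 and 60.69, that is 54 and 61. With 60 completers the power is 0.834.

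**2. What exclusion would cost, if it were the rule.** The documents give no out-of-window rate, so the following is illustration only. Assume exactly 60 completers, hence 60 × 2 = 120 one-month visits, and a one-month comparison (10.2 names no visit).

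- Five late visits in five different subjects: 5/120 = 4.2% of visits and 55 pairs left. The 95% confidence half-width, in SDs of the paired difference, is t(0.975, n − 1)/√n: 0.2583 at n = 60 and 0.2703 at n = 55. The ratio is 1.0465, so the interval is about 4.7% wider.
- If the same five subjects are late in both periods, it takes ten such visits to lose five pairs.
- With an independent chance q that each visit is out of window, the expected number of pairs is 60 × (1 − q)², rounded down below:

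| q | Pairs | Power for 0.5, SD 1.3 |
|---|---|---|
| 0 | 60 | 0.834 |
| 2% | 57 | 0.814 |
| 5% | 54 | 0.792 |
| 10% | 48 | 0.742 |
| 20% | 38 | 0.637 |

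The power column applies to the 0–10 subjective ratings, the only measure with sizing inputs. The visible text does not say when ratings are collected, and section 11.4 mentions take-home questionnaires, so they may not depend on these visits at all. Power passes below 80% at 55 pairs (0.7999), but that crossing has no special meaning when the rate is unknown and the number of completers is approximate.

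**3. Does the text require exclusion?** Set 7.4 beside 10.2. The first labels the visit. The second removes a point only when it is missing, and a grade recorded on day 33 is not missing. The sentence on evaluated participants speaks of people rather than visits, so it does not settle the matter, but it leans towards use. Both readings are open.

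**4. Are late visits expected to be common?** The window runs from day 24 to day 32, which is nine days. Section 7.4 also asks the investigator to confirm before enrolment that the subject can attend within the windows. The loose wording on rescheduling covers only the subject who comes without study lenses and has no problem with them; it is not a general allowance for late visits.

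**5. Visit 3.** The heading of 7.4.3 attaches the Day 28 window to the Pair 1 one-month visit and names the dispensing of Pair 2 after it. Sections 7.4.4 and 7.4.5 count their days from Pair 2, and the dispensing steps are those of Visit 1, which is Day 0 and has no window. The Pair 2 dispensing grades are therefore naturally Pair 2's Day 0, whatever the timing of Visit 3.

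**The case for a change.** The best case for a change is that a rule stated to be for analysis should have an effect in the analysis. If the label did nothing to the data it would be idle, so exclusion is what a reader would infer. The rule could then be settled when the report is written, with lens identity perhaps already known, and a few words now would prevent that.

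Part of this stands. The label's effect is undefined, and 10.2 does not fill the gap. But the label is not idle under the other reading: it can govern how visits are tabulated and which visit a value belongs to in the between-visit comparisons, and 7.4 uses the term in just that way when it counts attendance.

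The risk of a convenient choice is limited. Windows are fixed by day count, subject and investigator are masked, and 7.3.7 normally keeps the mask until the database is final. That detail is deferred to the report is a broader feature of 10.2 and not a separate fault in 7.4.

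Nor is one rule plainly better. Using every planned follow-up keeps more subjects. Using only in-window visits keeps wear time uniform, which may matter for deposits because no lens replacement is planned within the month.

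**Conclusion.** The ambiguity is real but small, and no change to the plan is needed. The documents do not say that out-of-window values are discarded, and 10.2 can as well be read to keep them. Either choice gives a sound paired comparison, provided that it is applied alike to both lenses and that lateness is unrelated to the lens worn, which is an assumption. The choice trades a little precision against uniform timing. Analysts would ordinarily settle it and report the number of affected visits per lens.

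Under the exclusion reading, with 60 completers and five pairs lost, the cost is a confidence interval about 4.7% wider. A rate of 10% or more per visit would cost appreciably more (48 pairs or fewer), but nothing in the documents points to such a rate, and the nine-day window and the check on attendance work against it. No power shortfall is shown. The worry about the Pair 2 dispensing grades is answered by the headings of 7.4.3 to 7.4.5.

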7.4.1 Visit 1: Screening / Baseline Visit / Dispensing Pair #1

Screening / Baseline

The following evaluations will be performed to assess eligibility according to the Inclusion and Exclusion Criteria at the Screening visit:

1. The subject is expected to attend the screening / baseline visit not wearing their habitual contact lens products for at least 12 hours prior to the study visit.
2. The subject will be required to read and sign an Informed Consent Form prior to enrolment. When the subject has signed the consent form, the subject will be considered to be enrolled on to the study.
3. Subject demographics and medical history (age, sex, race and ethnicity, medical conditions, medications, allergies) will be recorded by the investigator
4. Contact lens history (own lens information, rewetting drop use, and wear time)

5. Baseline monocular high illumination, high contrast (HIHC) entrance visual acuity with habitual spectacles or spectacle refraction
6. Auto refraction/auto keratometry: Flat and Steep K readings (D)
7. Sphero-cylindrical refraction (D), and best sphere refraction (D) & monocular & binocular distance visual acuity (HIHC) (logMAR)
8. The endpoint of this over refraction will be the best objective acuity, with (-) only being given with objective acuity, not subjective acuity improvement (not to the point that the letters start to shrink in size).

[REDACTED]

[REDACTED]

11. Slit lamp biomicroscopy will be assessed according to the guidelines set out in the CVI Grading scales (Appendix 2).
12. The investigator will confirm that the subject meets the criteria set out in the inclusion criteria, and none of the exclusion criteria and is eligible to continue in the study.
13. The subject will be assigned a randomization ID and the first pair of contact lenses (either test or control) will be selected according to the randomization table.
14. Initial contact lens power chosen based on vertexed, spherical equivalent obtained from refraction. The contact lens power will be kept the same for both test and control.
15. The contact lenses will be dispensed by a research assistant / study coordinator / technician (in a manner which does not unmask the subject and investigator).

Dispensing Pair #1

1. The lenses will be inserted by the subject from the blister pack. The use of saline for rinsing prior to insertion is permitted if necessary.

[REDACTED]

[REDACTED]

[REDACTED]

[REDACTED]

[REDACTED]

[REDACTED]

3. The lens fit will be assessed for fit acceptance (acceptable or not acceptable) and absence of lens defects. If the fit is acceptable and there are no defects, the subject will be allowed to sit for 10 minutes to allow for the lenses to settle.

4. [REDACTED]

5 [REDACTED]

6 [REDACTED]

7. [REDACTED]

8. Monocular lens surface and fit will then be assessed and graded according to the CVI grading scales (Appendix 2):

[REDACTED]

c. Lens wettability (0-4 scale)

[REDACTED]

f. Lens deposition (0-4) and deposit type

[REDACTED]

9. Monocular lens fit will be assessed and graded according to the CVI grading scales (Appendix 2). Lens fit will be video recorded in the event of poor fit.

[REDACTED]

b. Lens centration (optimal /slightly decentered, <0.5mm /extremely decentered >0.5mm, NTSI)

[REDACTED]

[REDACTED]

[REDACTED]

4. Monocular lens surface will then be assessed and graded according to CVI grading scales (Appendix 2).

[REDACTED]

c. Lens wettability (0-4 scale)

[REDACTED]

f. Lens deposition (0-4) and deposit type

[REDACTED]

5. Monocular lens fit will then be assessed and graded according to CVI grading scales (Appendix 2).

[REDACTED]

b. Lens centration (optimal /slightly decentered, <0.5mm /extremely decentered >0.5mm, NTSI)

[REDACTED]

[REDACTED]

i. Overall lens fit acceptance (0-4 scale, and yes/no) and investigator reason, if unacceptable.

[REDACTED]

[REDACTED]

7. Slit lamp biomicroscopy will be assessed according to the guidelines set out in the CVI grading scales. The same pair of contact lenses will be re-inserted.

8. The subject will be instructed to wear the study lenses for at least 8 hours per day, maximum of 16 hours per day and at least 5 days per week.

9. The subject will be discharged and reminded to return for the one-month visit.

7.4.3 Visit 3: One Month Visit Pair #1 (Day 28 ± 4)/Dispensing pair #2

Subjects will be asked to wear lenses for at least 2 hours prior to the visit appointment.

Subjects who attend without lenses in situ for at least two hours will be rescheduled.

The following procedures will be performed (any ocular measurement procedures outlined below will be carried out on each eye):

[REDACTED]

[REDACTED]

- 1. [REDACTED]
- 2. [REDACTED]
- 3. [REDACTED]
- 4. [REDACTED]
- 5. [REDACTED]
- 6. [REDACTED]
- 7. [REDACTED]
- 8. [REDACTED]
- 9. [REDACTED]
- 10. [REDACTED]
- 11. [REDACTED]
- 12. [REDACTED]
- 13. [REDACTED]
- 14. [REDACTED]
- 15. [REDACTED]

[REDACTED]

- 1. [REDACTED]
- 2. [REDACTED]
- 3. [REDACTED]
- 4. [REDACTED]

[REDACTED]

5. Monocular lens surface will then be assessed and graded according to CVI grading scales (Appendix 2).

- [REDACTED]
- [REDACTED]
- c. Lens wettability (0-4 scale)
- [REDACTED]
- [REDACTED]

- f. Lens deposition (0-4) and deposit type
- [REDACTED]

[REDACTED]

6. Monocular lens fit will then be assessed and graded according to CVI grading scales (Appendix 2).

[REDACTED]

b. Lens centration (optimal /slightly decentered, <0.5mm /extremely decentered >0.5mm, NTSI)

[REDACTED]

[REDACTED]

[REDACTED]

[REDACTED]

[REDACTED]

[REDACTED]

[REDACTED]

i. Overall lens fit acceptance (0-4 scale, and yes/no) and investigator reason, if unacceptable.

- [REDACTED]
- [REDACTED]
8. Slit lamp biomicroscopy will be assessed according to the guidelines set out in the CVI Grading scales.
9. There will be a 10-minute wash-out before insertion of pair 2.

Lens Dispensing Pair # 2

1. The second lens pair will be applied (according to the randomization table). The contact lenses will be provided by a study coordinator/technician to maintain masking of the investigator. The lenses will be inserted by the subject from the blister pack.
2. The use of saline for rinsing prior to insertion is permitted if necessary.
3. Lens powers of the second pair will be matched with the first pair if possible.

Procedures will be repeated as detailed in Visit 1 for pair 2 from section 7.4.1 (steps 1-13 in Dispensing pair#1 section).

7.4.4 Visit 4: Two-week follow up of pair #2 (Day 14 ± 3 of pair 2)

*Subjects will be asked to wear lenses for **at least 2 hours** prior to the visit appointment. Subjects who attend without lenses in situ for at least two hours will be rescheduled.*

Procedures will be repeated as detailed from section 7.4.2 for pair 2 (steps 1-9).

7.4.5 Visit 5: One Month Visit Pair 2/Study Exit (Day 28 ± 4 of pair 2)

Subjects will be asked to wear lenses for at least 2 hours prior to the visit appointment. Subjects who attend without lenses in situ for at least two hours will be rescheduled.

Procedures will be repeated as detailed from section 7.4.3 (steps 1-8).

[REDACTED]

[figure not shown]
- 1. [REDACTED]
- 2. [REDACTED]
- 3. [REDACTED]
- 4. [REDACTED]

[REDACTED]

3. Slit lamp biomicroscopy assessment will be conducted according to the guidelines set out in the CVI Grading scales
4. Exit visual acuity with habitual spectacles or spectacle refraction (using same method and refraction as entry).
5. The subject will be discharged and will sign the exit statement.

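### A randomized lens judged not acceptable on fit at insertion can be lost from the primary lens fit comparison under the rules in 10.2

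*Combined protocol and SAP*

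**What the plan says.** Section 2 lists "Lens fit performance" among the primary variables. It names no fit item, visit or summary measure.

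Under 7.4.1 the first pair is selected from the randomization table (screening step 13) before any fit is seen. Dispensing step 3 then reads: "The lens fit will be assessed for fit acceptance (acceptable or not acceptable) and absence of lens defects". It continues: "If the fit is acceptable and there are no defects, the subject will be allowed to sit for 10 minutes". Steps 4 to 7 are redacted. Surface grading is step 8 and fit grading is step 9, which adds: "Lens fit will be video recorded in the event of poor fit". For the second pair, 7.4.3 says: "Procedures will be repeated as detailed in Visit 1 for pair 2 from section 7.4.1 (steps 1-13 in Dispensing pair#1 section").

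The follow-up visits include "Overall lens fit acceptance (0-4 scale, and yes/no) and investigator reason, if unacceptable". Section 7.4 permits a scheduled follow-up lens assessment only when the subject arrives in the study lenses.

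On analysis, 10.2 says: "Paired t test will be used to compare slit lamp biomicroscopy, lens fit and subjective scores between study lens types". It takes in everyone who was evaluated, and then: "In the event of missing data, individual data points will be excluded in the analysis and not extrapolated from the collected data". It leaves the detailed analysis plan to the report.

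**The concern.** Step 3 acts after randomization, separately for each lens, and on a variable that is itself primary. The lenses that do worst on that variable are the ones least likely to have a grade to compare. Their absence would be informative: the score is missing because the fit was poor.

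If the test lens fails at insertion more often than the control, a comparison restricted to graded lenses would understate the difference. The two lenses would look more alike than they are. That matters most for any non-inferiority test, which 10.2 foresees where appropriate without tying it to fit or giving a margin.

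The losses would also be hard to notice. Section 7.1 allows up to 80 subjects dispensed for 60 completed and does not replace those who discontinue. A few insertion failures would sit unremarked among the 80 − 60 = 20 subjects already allowed for.

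**Working it through.** **The plan's own figure.** Table 3 in 10.1 gives 56 subjects (80% power) and 63 (85% power) for a mean difference of 0.5 with SD 1.3. A paired t test at two-sided 0.05, by the noncentral t distribution, reproduces both: power 0.807 at 56 and 0.852 at 63. That calculation concerns subjective ratings on a 0-10 scale. It gives no rate of unacceptable fit and no fit score, so it cannot size this point.

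**Path of a lens that fails on fit at step 3.**

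1. It is a randomized lens (7.4.1, screening step 13), so its loss is a loss after randomization.
2. Step 3 records it as not acceptable. The readable text sends only acceptable, defect-free lenses on to settle. It does not say what follows for the others.
3. If it is not dispensed, 7.4 rules out a two-week or one-month lens assessment, because the subject cannot attend wearing it. Table 1 lists one base curve (8.6 mm) and one diameter (14.2 mm) per lens, so it shows no second geometry of the same lens.
4. Its follow-up fit scores are then missing, and 10.2 excludes missing points.
5. A paired t test needs a score on both lenses, so the subject's fit score on the other lens leaves that test too.
6. The step 3 yes/no result survives in the record, but 10.2 gives it no place in the comparison.

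**Size, by illustration only.** Let fT and fC be the proportions failing at step 3 on test and control, and g the gap in mean grade between accepted and failed lenses. Assume that accepted lenses grade alike on both types and remain acceptable, that g is the same for both, and that failures are independent between lenses. Then:

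- difference among graded lenses = 0
- difference over all inserted lenses (test − control) = −(fT − fC) × g
- complete pairs from 60 subjects = 60 × (1 − fT) × (1 − fC)

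Take g = 3.8 − 1.0 = 2.8 on a 0-4 scale. Both means are assumed, with higher taken as better; Appendix 2, which defines the scales, is not available.

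| Assumed fT / fC | Hidden difference in acceptance | Hidden difference in grade | Complete pairs |
|---|---|---|---|
| 2% / 2% | 0 points | 0.00 | 60 × 0.98 × 0.98 = 57.6 |
| 5% / 2% | −3 points | −0.03 × 2.8 = −0.08 | 60 × 0.95 × 0.98 = 55.9 |
| 10% / 2% | −8 points | −0.08 × 2.8 = −0.22 | 60 × 0.90 × 0.98 = 52.9 |
| 20% / 5% | −15 points | −0.15 × 2.8 = −0.42 | 60 × 0.80 × 0.95 = 45.6 |

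With no control failures and g = 3, test failure rates of 2%, 5% and 10% hide 0.06, 0.15 and 0.30 grade. A rate of 5% is 0.05 × 80 = 4 subjects, if all 80 reach the test lens.

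The first row carries the limit of the point: equal failure rates cost pairs but do not bias the difference.

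**The case against.** The case on the other side is substantial.

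- **Redaction.** Steps 4 to 7 are redacted. The reference in 7.4.3 to steps 1-13 implies steps 10 to 13, which cannot be read either. What happens to a subject whose lens fails may be set out there, so its absence from the readable text is not an omission. This stands. It does not settle the analysis rule, because the relevant text of 10.2 is readable and gives no value to a step 3 failure.
- **Reach of the condition.** The sentence in step 3 conditions only the settling period, and the poor-fit provision in step 9 shows that poor fits were expected at grading. This stands against any claim that only good fits are ever graded. It is also consistent with a lens that passes at insertion and settles badly, so it does not show that step 3 failures are graded.
- **Step 3 is itself a fit outcome.** A subject judged there was evaluated, and 10.2 uses everyone evaluated. This too stands, and it makes the remedy cheap. It does not supply the missing half of a pair in a t test of scores.
- **Defects.** Section 7.3.5 provides for replacing a damaged or defective lens, so a defect need not cost the eye its grade. Accepted: the point concerns fit failures only.
- **Equal rates are plausible.** Both lenses have the same nominal base curve, diameter and power range. This makes a large difference in failure rates less likely but does not exclude one.

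A reader might go further and infer that failed lenses certainly drop out, or that both lenses must then look close to perfect. The documents support neither. The fate of a failed lens may be redacted, and no fit distribution is given. A yes/no pass before settling does not fix centration or later grades, and follow-up grading expressly allows for unacceptable fits.

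**Conclusion.** The concern holds in a limited form. For a lens not dispensed because of poor fit, the requirement in 7.4 to attend in the study lenses, the exclusion of missing points and the paired test together remove it from any comparison of follow-up fit scores. Nothing readable in 10.2 brings it back through the step 3 result. Because the detailed analysis plan is left to the report, the handling could also be settled after the results are known.

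The direction is conditional. If insertion failures differ by lens type, the comparison is biased towards similarity. If the rates are equal and a failed lens falls short by the same amount on each type, the difference is unbiased. The size is unknown: every failure rate and grade gap used above is an assumption, and nothing in the documents shows that the rates do differ. The conclusion also rests on failed lenses not being dispensed, which the readable text suggests but does not state.

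**What to change.** In 10.2:

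1. Name the fit variable and visit that are primary. Compare fit acceptance (yes/no) by lens type over every eye in which a randomized lens was inserted, with a method that respects the pairing and the two eyes per subject.
2. Count a step 3 result of not acceptable for fit as not acceptable for that lens, and keep the subject's data on the other lens where they exist.
3. Keep lens defects separate from fit failures.
4. Tabulate step 3 results by lens type.
5. Show the paired comparison of graded eyes alongside. Use a worst-grade score for failed lenses only as a sensitivity analysis, since it assigns a grade to a lens that was not worn and sits uneasily with the no-extrapolation rule in 10.2.

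If the redacted steps already fix how a failed lens is recorded, 10.2 need only refer to them and state how the result is counted.

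The cost is some wording and one derived variable. Step 3 already records the result, so no new data are needed. The downside is that the fit result may look slightly less favourable.
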